5.3.2.1.6 MDS-UPDRS Part II subscale: difference in mean at 12 and 18 months

Definitions of endpoints

The endpoint for each participant is MDS-UPDRS Part II score measured bi-monthly over 18 months or up to the start of ST, including Baseline score and scores at 2, 4, 6, 8, 10, 12, 14, 16 and 18 months.

Main analytical approach

Details on the ICE handling for these estimands can be found in [Section 1.2](#). All data recorded after a participant initiates ST will be censored.

A LMEM for longitudinal analysis of covariance (ANCOVA)/repeated measures will be applied to all data recorded up to Month 18. This LMEM will use the same modelling approach described in [Section 5.3.1.4.1](#) (baseline Part II score will be used in place of Part I-III sum score).

A summary table presenting treatment effect estimates (based on the treatment by time interactions) and corresponding 95% CIs will be produced. The estimates at 8, 10, 12 and 18 months will be the main results to be interpreted.

Plots displaying the adjusted means and 95% confidence intervals for each treatment group from the above model will be produced.

Sensitivity analyses

This model will be refit using log-transformed data, as the normality assumption for the residuals does not appear to hold for this subscale when analyzing the PPMI data (UCB internal observation). If the participants Part II sum score is 0, the log-transformed score will be calculated as $\log(0.1)$. The same summary outputs will be produced as for the main analysis, results will be back-transformed to aid interpretability.

Supplementary analyses (regardless of ST initiation)

As a supplementary analysis, the model will be fitted again using a different ICE handling strategy for ST initiation. Here ST will be handled using a “treatment policy” strategy where post-ICE data is kept as part of the analysis. This supplementary analysis will be carried out on log-transformed data. The same summary outputs will be produced as described for the main analysis.

5.3.2.1.7 MDS-UPDRS Part II subscale: emerging symptoms within 18 months

Emerging symptoms

Definitions of endpoint

The emerging symptoms based on MDS-UPDRS Part II (Tosin et al., 2022) for individual participants are derived using the following steps:

- 1) Identify the symptoms not present at Baseline, ie, MDS-UPDRS Part II items with score ‘0’ at Baseline.
- 2) For the items identified in step 1, calculate change from Baseline at each visit. The participant is considered to have an emerging symptom for the item (or event), if the change from Baseline for the item is greater than 0 for 2 consecutive visits or if symptomatic therapy was initiated between the first visit identified as showing a change greater than 0 and the following visit with a recorded score. The magnitude of change from Baseline will not be considered to determine the emerging symptom.

- 3) The participant-level endpoint will be derived as the total number of emerging symptoms identified in step 2.
- 4) The participant-level annualized rate of events is calculated as total number of emerging symptoms calculated in step 2 divided by total duration of follow-up.

Main analytical approach

The main ICE will be initiation of ST, this will be handled using a “composite” strategy. When the ST is initiated before the occurrence of the event this will be ignored. Initiation of ST between the emergence of a symptom for an item and the following visit is part of the endpoint definition.

All occurrences of important protocol deviations with long-term impact, death, study termination and loss to follow up, will be ignored (ie, rate of occurrence of the events is calculated only for the observed duration therefore introducing a small bias on the estimate of annualized rate of events). Missed visits and important protocol deviations with short-term impact will also be ignored. Treatment discontinuation and COVID-19 related ICEs will be handled in the same way as described for other MDS-UPDRS endpoints.

The population-level summary will be the ratio of annualized rate of emerging symptoms based on MDS-UPDRS Part II over 18 months period between:

- UCB0599 high dose (360mg/day) and placebo
- UCB0599 low dose (180mg/day) and placebo

The annualized rates will be estimated using a negative binomial regression model with a fixed treatment effect and the log of the observed duration in study as off-set. The model will include gender and age as covariates and log of observed duration as off-set.

Estimates for the treatment effects of interest (see above) over the 18-month period adjusted for gender and age at Baseline with corresponding 95% CI.

To support the interpretation of these analyses, a summary table will be produced showing the number and percentage of study participants who experienced 0, 1, 2, ... and up to 13 emerging symptoms/events over 18 month by treatment group.

Supplementary Analyses:

Alternative ST initiation handling strategy

The same analysis will be repeated as above but using a “Treatment policy” handling strategy for ST initiation, i.e. the definition of the endpoint will be altered so that ST initiation will no longer be considered when determining an emerging symptom.

Alternative Part II endpoint (symptoms worsening)

Definitions of endpoints

The participant-level endpoints will be the time from Baseline to the participant’s *first* 3-point increase in MDS-UPDRS Part II subscale (or to last observed time prior to ST initiation) within the 18-month period, where the 3-point increase is confirmed at the next visit record or ST is initiated before the next visit record.

ICE Handling Strategies

Full details on the ICEs handling for this estimand can be found in [Section 1.2](#). The main ICE will be initiation of ST, this will be handled using a “composite” strategy where initiation of ST is part of the endpoint definition. Study termination and loss to follow up related to treatment “lack of efficacy” will be handled by using non-responder imputation (considered as an event). All other occurrences of study termination and loss to follow up will be right-censored, i.e., analysis only takes account of events which occurred within the observed duration.

Population Summary

The population level summary will be the difference in target population restricted mean event time (RMET) up to the last observed event (or last observed time prior to ST initiation) between:

- UCB0599 high dose (360mg/day) and placebo
- UCB0599 low dose (180mg/day) and placebo

In this study, the RMET can be interpreted as the average time to the above defined event-based endpoint.

Estimator

This analysis will use the same modelling approach as described for the MDS-UPDRS Part II subscale time to worsening analysis (see [Section 5.3.2.1.5](#) for further details).

Estimates

A summary table presenting the adjusted difference in RMET of the *first* 3-point increase in MDS-UPDRS Part II subscale between each UCB0599 treatment group and placebo and the corresponding 95% CIs will be produced, this summary will also include the model estimates of adjusted RMET for each treatment group.

To support the interpretation of these analyses, a summary table will be produced showing the number and percentage of study participants who reach this endpoint by treatment group and visit. A listing will also be produced showing date and type of event (i.e. 4 options: confirmed *first* 3-point increase, *first* 3-point increase followed by ST initiation, ST initiation only, or treatment-related “lack of efficacy” study termination) for each participant, based on the FAS.

Sensitivity analyses

The RMET will be estimated for each combination of treatment group and gender as the area under the Kaplan-Meier “survival” curve up to the last observed event time (ie, without using a modelling approach). A plot of these Kaplan-Meier curves will be produced, with the RMET estimates also included in the figure. These results can be used to assess the proportional hazards assumption as well as for comparison to the results using the modelling approach. Results from the log rank test (testing the null hypothesis that there is no difference between the six survival curves) will also be displayed on this plot.

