5.3 Efficacy estimands and endpoints

All efficacy data will be listed based on the FAS. All summaries and analyses for efficacy estimands and endpoints will be presented for the FAS.

Statistical outputs

For all statistical models fitted to the efficacy data, diagnostic plots will be included in the statistical output documents. The statistical outputs for all models will include the following treatment group comparisons:

- a. UCB0599 high dose (360mg/day) versus placebo,
- b. UCB0599 low dose (180mg/day) versus placebo,

For some key analyses (defined elsewhere), the model output summary table will also present the percentage change in mean slope or in mean difference at Month 12/18 for each dose-level against placebo (ie, the difference in slope/mean divided by the placebo slope/mean multiplied by 100).

For some key analyses (defined elsewhere), the mean slope or the mean difference at Month 12/18 for each dose-level against placebo will be depicted in forest plots with either corresponding 95% CIs or 80% CIs, the latter to match the type I error used in the trial sample size estimation.

MDS-UPDRS score derivation

For all MDS-UPDRS analyses, MDS-UPDRS Part I-III and subscales (Part I, Part II, Part III) sum scores will only be calculated if responses are available for all questionnaire items. If one item response is missing, for example in Part I, Part II and Part III sum scores can still be calculated but Part I and Part I-III sum scores will not be calculable. However, missing responses to individual items within the questionnaire are not expected.

To calculate the sum scores, the response scores to the following items will be summed:

- Part I: items 1.1 to 1.13, sum score ranges from 0 to 52;
- Part II: items 2.1 to 2.13, sum score ranges from 0 to 52;
- Part III: items 3.1 to 3.18 (for Part III some items will be tested on both side of the body and on the upper as well as the lower limb – all responses will be summed to get the Part III total score, 33 items in total), sum score ranges from 0 to 132;
- Part I-III: items 1.1 to 1.13, 2.1 to 2.13 and 3.1 to 3.18, sum score ranges from 0 to 236.

When MDS-UPDRS is collected at home rather than in clinic not all MDS-UPDRS data will be collected (rigidity assessments will be missing) and the Part III and Part I-III sum scores cannot/will not be calculated. Part I and Part II sum scores can still be calculated and used in any analyses, assuming all item responses are collected.

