Symptomatic Treatment Status and other ICES

For all summary tables and listings where ST status is used or presented, the assumption is made that once a participant starts ST, they remain on ST for all study visits after their initiation date.

For summary tables that are being presented for participants who are not yet on ST, this means not yet on ST by a particular visit. This means that the number of participants contributing to the summary will differ by visit in the table, as more participants may have initiated ST by the following visit.

For plots that are displayed by ST initiation timing, the following categories will be defined for participants who started ST:

- By month 2 (inclusive);
- between month 2 and 4 (inclusive);
- between month 4 and 6 (inclusive);
- between month 6 and 8 (inclusive);
- between month 8 and 10 (inclusive);
- between month 10 and 12 (inclusive);
- between month 12 and 18 (inclusive);
- not started by 18 months/EOT.

To support the efficacy analyses presented in this section, a (cumulative) summary table presenting the number and percentage of participants with each ICE (see [Section 1.2](#) for a full list of the ICEs defined in this study) will be produced by visit.

Modelling considerations

Baseline covariates

For any analyses adjusting for continuous covariates, these covariates will be mean centered to aid interpretability (the intercept term can be interpreted as the expected value of the response when the dependent variables are set to their means). When mean centering covariates, the calculated mean will be based on the data used for that estimand analysis. All efficacy models will include age at baseline as a covariate. Since this study was randomized stratifying for gender, gender should be included as a covariate in all efficacy models unless explicitly stated otherwise.

As stated in [Section 4](#), for all analyses, a participant should only be included in the model if they have a baseline score for the endpoint being analyzed.

Estimation considerations and Convergence issues

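### The Part II emerging-symptoms model does not adjust for the number of items at zero at Baseline: a possible loss of precision, not a bias

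*SAP*

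**What the plan says.** SAP 5.3.2.1.7 builds the endpoint in steps. Step 1 is to "Identify the symptoms not present at Baseline, ie, MDS-UPDRS Part II items with score" 0. Step 2 classes each of those items as emerged or not, and "The magnitude of change from Baseline will not be considered to determine the emerging symptom". Step 3 sums them: "The participant-level endpoint will be derived as the total number of emerging symptoms identified in step 2". The participant's rate is this count divided by follow-up time.

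On the model, the SAP says "The annualized rates will be estimated using a negative binomial regression model with a fixed treatment effect", and then "The model will include gender and age as covariates and log of observed duration as off-set". Protocol 9.3.1.2.4 has the same covariates and offset.

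The general modelling rule in SAP 5.3 adds nothing about baseline Part II. It says "All efficacy models will include age at baseline as a covariate" and asks for gender because randomization was stratified by it. The supplementary analysis of the same count changes only how initiation of symptomatic treatment (ST) is handled. The supporting table shows participants who "experienced 0, 1, 2, ... and up to 13 emerging symptoms/events over 18 month by treatment group", with no split by the number of items at risk.

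Other models in the plan do carry a baseline term for their own outcome. These are the Part II mean model (SAP 5.3.2.1.6), the repeated-measures models for the Parts I-III sum score, Part III and Part I, the MoCA model (5.3.2.2.2) and the DaT-SPECT model (5.3.2.3.2).

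**The concern.** Take two participants in the same arm, of the same age and gender and followed for the same time. One has 4 Part II items at 0 at Baseline and the other has 12. The first can have at most 4 events and the second up to 12, yet the model gives them the same expected count. The difference between them goes into the dispersion parameter, and that widens the interval for the rate ratio.

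The information is already in hand. Step 1 derives K, and SAP section 4 excludes participants with a missing baseline assessment for the endpoint. Randomization is stratified by gender only (SAP 1.3), so K is not balanced by design. SAP section 2 asks readers to weigh effect sizes and confidence intervals rather than p-values, so avoidable width matters for this listed secondary estimand.

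**Working it through.** **The bound.** SAP 5.3 gives the item list: "Part II: items 2.1 to 2.13, sum score ranges from 0 to 52", which is 13 items. Events come only from the K items at 0, at most one per item, so 0 ≤ count ≤ K ≤ 13.

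**No figure to reproduce.** The plan states no power, event rate or dispersion for this endpoint. The only planning figure used is 143 per arm. It follows from the formula in SAP 3.1 with the Table 3-1 inputs: ρ = 154.0/185.1, r_τ = 0.43/185.1, Δ² = 0.27²/185.1, and

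n = 2 × [(1 − ρ) + r_τ × 85.57] × 2.56² / (85.57 × Δ²) = 142.66, ie 143.

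**Simulation.** There were 300 trials per scenario with 143 per arm. The count was drawn as Binomial(K, 1 − exp(−h × frailty × RR × duration)). Every input below is assumed:

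- K mean 6 or 8, SD 1.5 or 3, clipped to 0-13
- per-item hazard h of 0.1 or 0.2 per year, independent of K
- gamma frailty variance 0.3 or 1.0
- RR 1.0 or 0.7
- 25% leaving early

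Each trial was fitted with the planned model and again with log(K) added.

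| Quantity | Result |
|---|---|
| SE of log RR, K SD 3 | 3% to 13% lower with K |
| SE of log RR, K SD 1.5 | 1% to 3% lower with K |
| Estimated RR, with versus without K | differs by at most 0.005 |
| Type I error without K (nominal 0.05) | 0.02 to 0.07, Monte Carlo SE 0.013 |
| Power at RR 0.7, K SD 3 | 0 to 12 points higher with K, Monte Carlo error about 3 points |
| Participants with K = 0 | 0% to 3.4% |

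In variance terms, the largest SE reduction is 1 − 0.87² = 0.24, ie 24% lower. Put the other way round, leaving K out makes the variance 1/0.87² = 1.32 times as large, ie 32% higher. Separate runs with K mean 8 and SD 2.8 gave model variance 7% to 13% lower. Empirical variance ratios in two of those settings were 0.90 and 0.99, ie 10% and 1% lower.

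**Why the spread of K matters.** The omitted factor adds roughly its squared coefficient of variation to the dispersion. That is (2.8/8)² = 0.12, (3/6)² = 0.25 and (1.5/8)² = 0.035, to be set against frailty variances of 0.3 and 1.0.

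**If the per-item hazard depends on K** (K mean 8, SD 2.8):

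| Per-item hazard | log(K) as covariate: model variance | log(K) in the offset: model variance |
|---|---|---|
| independent of K | 7% to 13% lower | similar to the covariate |
| falls as K^-0.5 | 3% to 5% lower | 0% to 2% lower |
| falls as 1/K | about unchanged | about 10% to 12% higher |

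This pattern is expected. With hazard proportional to K^-γ, the expected count goes as K^(1−γ). At γ = 0.5 the contribution of K shrinks to about a quarter, and at γ = 1 it vanishes. An offset forces the coefficient to 1 even when the true value is 0, so it adds variance.

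**The case against.** The case for leaving the model alone has four parts.

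1. **The model is valid for its stated target.** That target is a ratio of annualized rates per participant. K is a baseline variable in a randomized comparison, and protocol and SAP agree with each other. This stands. A reader might infer that the rate ratio is biased or the test anticonservative because K caps the count. The documents do not support that, and the simulations show neither.

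2. **The gain is uncertain.** Participants with few items at 0 already have more symptoms and may acquire new ones faster. If so, the benefit shrinks, possibly to nothing. This stands, and no single percentage should be quoted.

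3. **Putting K into the offset is not a safe equivalent.** It can raise the variance, and it changes the target to a rate per item at risk. A reader might think the cap calls for it, but the plan defines a rate per participant-year. This stands. Nor does any form of K in the model remove the ceiling. With a true per-item RR of 0.7, estimates were 0.71 to 0.75 with or without K.

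4. **The stakes are low.** This is one non-key secondary estimand in a study that its own SAP calls exploratory. Baseline Part II is summarized by arm (SAP 6.1.1.2), and the Part II mean model adjusts for it. This is fair, but a summary by arm shows an imbalance without correcting it, and the other model addresses a different estimand.

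None of this argues against a covariate with an estimated coefficient. That form did no material harm in any setting tried.

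**Conclusion.** The point holds as a matter of efficiency and consistency. K is known before treatment, caps the outcome and is absent from the model in both documents, while the plan's other models of Part II, MoCA and DaT-SPECT adjust for baseline. The cost of leaving it out lies between nothing and a moderate loss of precision. Where it falls depends on the spread of K and on how the per-item hazard relates to K, and the documents give neither. The omission also leaves the estimate exposed to chance imbalance in K. The primary analysis is not touched. The change is worth making, but the planned analysis is not invalid without it.

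**What to change.** Before the study team is unblinded, amend SAP 5.3.2.1.7 as follows:

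- Add K as a baseline covariate with an estimated coefficient, in a form defined at zero, such as K itself or log(K+1). Plain log(K) is undefined at K = 0 and would drop those participants.
- Keep log of observed duration as the only offset, so that the target remains a rate per participant-year. Do not put K in the offset.
- State how participants with K = 0 are handled. Their count is 0 by construction, and neither document mentions them. Keeping them in the model is consistent with using the FAS for all efficacy analyses.
- Optionally, show the supporting table of event counts by K.

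Apply the same covariate to the supplementary analysis that changes the ST handling. Record the difference from Protocol 9.3.1.2.4 in SAP Appendix 2. The cost is one derived variable and a few sentences; no new data are needed.

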5.3.2.1.8 MDS-UPDRS Part I subscale: difference in mean at 12 and 18 months

Definitions of endpoints

The endpoint for each participant is MDS-UPDRS Part I score measured bi-monthly over 18 months or up to the start of ST, including Baseline score and scores at 2, 4, 6, 8, 10, 12, 14, 16 and 18 months.

Main analytical approach

Details on the ICE handling for these estimands can be found in [Section 1.2](#). All data recorded after a participant initiates ST will be censored.

A LMEM for longitudinal analysis of covariance (ANCOVA)/repeated measures will be applied to all data recorded up to Month 18. This LMEM will use the same modelling approach described in [Section 5.3.1.4.1](#) (baseline Part I score will be used in place of Part I-III sum score).

A summary table presenting treatment effect estimates (based on the treatment by time interactions) and corresponding 95% CIs will be produced. For the analysis over 12 months, the estimates at 8, 10 and 12 months will be the main results to be interpreted. The estimates at 8, 10, 12 and 18 months will be the main results to be interpreted.

Plots displaying the adjusted means and 95% confidence intervals for each treatment group from this model will be produced.

Sensitivity analyses

As a sensitivity analysis, the model will be refit using log-transformed data, as the normality assumption for the residuals does not appear to hold for this subscale when analyzing the PPMI data (UCB internal observation). If the participants Part I sum score is 0, the log-transformed score will be calculated as $\log(0.1)$. The same summary outputs will be produced as for the main analysis.

Other secondary estimand analysis (regardless of ST initiation)

For this secondary estimand, the model will be fitted again using a different ICE handling strategy for ST initiation. Here ST will be handled using a “treatment policy” strategy where post-ICE data is kept as part of the analysis. This analysis will be carried out on log-transformed data. The same summary outputs will be produced as described for the main analysis.

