#### Population-level summary

Difference in population mean MDS-UPDRS Parts I/II/III subscale at 18 months, in the absence of concomitant ST intake for Part II/III, or regardless of concomitant ST initiation for Part I between:

- UCB0599 high dose (360mg/day) and placebo
- UCB0599 low dose (180mg/day) and placebo

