### Estimates

Estimates for the treatment effects of interest (see above) at 18 months (MDS-UPDRS units difference) adjusted for gender and age at Baseline, with corresponding 95% CIs.

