### Sensitivity analyses

For MDS-UPDRS Part I and II, the main models will be refit using log-transformed data, as the normality assumption for the residuals does not appear to hold for this subscale when analyzing the PPMI data (UCB internal observation).

The main model for Part II and Part III will be refit, adjusting for Baseline predictors of early initiation of ST. For MDS-UPDRS Part II this analysis will be performed on log-transformed data. This sensitivity analysis will not be performed for Part I.

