##### Estimator, estimates, and sensitivity analyses

As per Supplementary Efficacy Estimand (Section 9.3.1.2.1.1). For MDS-UPDRS Part II, this supplementary analysis will be carried out on log-transformed data.

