**Table 9-2: Overview of handling strategies for MDS-UPDRS ICEs and study termination**

MDS-UPDRS Part I-III sum score and Part I/II/III subscales			
Estimand	Primary, key secondary and secondary	Key secondary	Secondary and supplementary
	In the absence of ST	Initiation of ST as part of the response	Regardless of ST
Population summary measure	
For Part I-III sum score: Difference in slope of progression at 12 months (primary) and difference in mean at 18 months (key secondary)
 
For Part III subscale: Difference in slope of progression at 12 months (key secondary)
 
For Part III subscale and Part III ePD subscore: Difference in mean at 18 months (key secondary)
 
For Part I/II subscale: Difference in mean at 12 and 18 months (secondary)
	
For Part III subscale: Difference in RMET (time to first 5-point increase) within 18 months (key secondary)
	
For Part I-III sum score: Difference in mean at 12 and 18 months (supplementary)
 
For Part II/III subscales: Difference in mean at 12 and 18 months (supplementary)
 
For Part II subscale: Ratio of annualized rates in emerging symptoms within 18 months (secondary)
 
For Part I subscale: Difference in mean at 12 and 18 months (secondary)

ICE			
Symptomatic treatment a	Hypothetical (set post-ICE data to missing)	Composite (ICE is part of the endpoint)	Treatment policy (include post-ICE data)
AE-related treatment discontinuation	Treatment policy (include post-ICE data)	id	id
Treatment discontinuation	Treatment policy (include post-ICE data)	id	id

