	
• Difference between UCB0599 and placebo in target population mean in MDS-UPDRS Part III ePD subscore at 18 months in the absence of concomitant ST intake• Ratio between UCB0599 and placebo based on population annualized rate of emerging symptoms assessed by MDS-UPDRS Part II subscale over the 18-month period• Difference between UCB0599 and placebo in target population mean MDS-UPDRS Part I subscale at 12 months regardless of concomitant ST intake• Difference between UCB0599 and placebo in target population mean MDS-UPDRS Part I subscale at 18 months regardless of concomitant ST intake• Difference between UCB0599 and placebo in target population mean observed MoCA at 18 months, regardless of concomitant ST intake 
Exploratory Efficacy Endpoints
 
• Time to worsening on MDS-UPDRS Part I subscale• Modified Hoehn and Yahr staging• CGII• CGIS• Fatigue-PRO• Early PD Function Slowness PRO• Early PD Mobility PRO• Composite endpoint (based on MDS-UPDRS and/or Early PD PROs)• PGIS, overall and fatigue-specific• PGIC, overall and fatigue-specific• SE-ADL• HADS• MDS-NMS• Starkstein Apathy Scale

Table 1-1: Study objectives

Objectives	Estimands
	
 • EQ-5D-5L • Wearable sensor

Secondary Efficacy Objectives
 
To demonstrate the superiority of UCB0599 over placebo with regard to neurodegeneration of dopaminergic neurons over 12 and 18 months in participants diagnosed with early-stage PD
	
Secondary Efficacy Estimand
 
 • Difference between UCB0599 and placebo in target population mean change from Baseline (Screening) in DaT-SPECT mean Striatum SBR at 18 months regardless of concomitant ST intake • Difference between UCB0599 and placebo in target population mean change from Baseline (Screening) in DaT-SPECT mean Striatum SBR at 12 months regardless of concomitant ST intake 
Exploratory Efficacy Endpoints
 
 • DaT-SPECT mean SBR in striatal subregions • CSF total ASYN • CSF ASYN oligomers/seeding capacity

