Population summary measure	For Part I-III sum score: Difference in slope of progression at 12 months (primary) and difference in mean at 12	For Part III subscale: Difference in RMET (time to confirmed first 5-point increase or ST	For Part I-III sum score: Difference in mean at 12 and 18 months (supplementary)

Table 1–2: Overview of handling strategies for ICEs, ICE-like protocol deviations and study termination or loss to follow-up for MDS-UPDRS estimands

	
and 18 months (key secondary and supplementary)^a
 
For Part III subscale: Difference in slope of progression at 12 months (key secondary)
 
For Part III subscale and Part III ePD subscore^a: Difference in mean at 12 and 18 months (key secondary)
 
For Part I/II subscale: Difference in mean at 12 and 18 months (secondary)
	
initiation) within 18 months (key secondary)
 
For Part II subscale: Difference in RMET (time to confirmed first 3-point increase or ST initiation) within 18 months (supplementary)
	
For Part I/II/III subscales: Difference in mean at 12 and 18 months (supplementary)

ICE & ICE-like protocol deviations			
ST initiation (Non-MAO-B Inhibitors) ^c	Hypothetical (set to missing & impute all post ICE visit data – MAR/ML)	Composite (ICE is part of the endpoint)	Treatment policy (Include post-ICE data)
ST initiation (MAO-B Inhibitor) ^c	Hypothetical (set to missing & impute all post ICE visit data – MAR/ML)	Composite (ICE is part of the endpoint)	Treatment policy (Include post-ICE data)
Treatment discontinuation (Lack of efficacy or AE)	Treatment policy (Include post-ICE data)	id	id
Treatment discontinuation (Other causes)	Treatment policy (Include post-ICE data)	id	id
Important ICE-like protocol deviations			
with long-term impact ^d	Hypothetical (set to missing & impute all post ICE visit data – MAR/ML)	Hypothetical (set to missing & treat as right-censored (non-event) at time of initial IPD)	id
With short-term impact ^d	Hypothetical (set to missing & impute single post-ICE visit data – MAR/ML)	Hypothetical (ignore)	id

Table 1–2: Overview of handling strategies for ICEs, ICE-like protocol deviations and study termination or loss to follow-up for MDS-UPDRS estimands

Death or serious injury (all causes)	Actual missing: impute all post ICE visit data – MAR/ML	Actual missing: treat as right-censored (non-event) at time of termination	id

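### The secondary Part I estimand regardless of ST is a difference in means, but the SAP analyses it only on log-transformed scores

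*SAP*

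**What the plan says.** SAP Table 1-1 lists as a secondary estimand "Difference between UCB0599 and placebo in target population mean MDS-UPDRS Part I subscale at 18 months regardless of concomitant ST intake", and a matching one at 12 months. A note under the table sends both to Section 5.3.2.1.8. SAP Table 1-2 and Protocol Table 9-2 also give the population summary as a difference in means at 12 and 18 months.

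SAP 5.3.2.1.8 contains three model fits for Part I:

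- The main analysis uses untransformed scores and censors data after ST initiation.
- A sensitivity analysis refits that model on log scores, with a zero score entered as log(0.1).
- The other secondary analysis keeps post-ST data. For this one the SAP says "This analysis will be carried out on log-transformed data", with the same outputs as the main analysis.

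Protocol 9.3.1.2.3 handles ST by treatment policy for Part I at Month 18; its population summary reads "or regardless of concomitant ST initiation for Part I between" each dose and placebo. The estimates are to be given "at 18 months (MDS-UPDRS units difference) adjusted for gender and age at Baseline, with corresponding 95% CIs". Logs enter only under sensitivity analyses, where "the main models will be refit using log-transformed data" for Parts I and II. The protocol does put one regardless-of-ST analysis on the log scale, but for another subscale (9.3.1.2.3.2): "For MDS-UPDRS Part II, this supplementary analysis will be carried out on log-transformed data".

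**The concern.** The estimand and its estimator are on different scales. A model for log scores compares mean logs between arms. Back-transformed, that is a ratio of geometric means, not a difference in arithmetic means. Converting it to Part I points needs further assumptions about the shape of the score distribution in each arm.

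If the plan is followed as written, a named secondary estimand is reported as a different quantity from the one defined. It also cannot be set in points beside the absence-of-ST result in the same section, so the effect of the ST strategy cannot be read in scale units. SAP Appendix 2, which lists departures from the protocol, does not mention the change of scale. Its only entry on these Part I estimands is struck out and concerned their classification.

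**Working it through.** There is no figure in the plan to reproduce. The check is a comparison of texts, followed by illustrations.

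**1. Is there an untransformed treatment-policy model for Part I anywhere in the SAP?** No. The untransformed model in 5.3.2.1.8 censors post-ST data and so targets the other Part I estimand. SAP 5.3.1.1 tabulates raw Part I means by arm and visit, overall and by ST status, but these are descriptive: no adjustment, no between-arm difference, no CI.

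**2. Is the log-scale result converted?** SAP 5.3.2.1.6 states back-transformation for the Part II log sensitivity analysis. SAP 5.3.2.1.8 does not state it for Part I. The zero rule is written under the Part I sensitivity analysis; that it also governs the treatment-policy model is the natural reading but is not stated.

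**3. Can a log contrast stand in for a difference in means?** Constructed example: everyone in arm A scores 5; in arm B, 10% score 0, 40% score 5 and 50% score 6.

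- Mean of B = 0.1×0 + 0.4×5 + 0.5×6 = 5.0, so the difference in means is 0.
- Log difference with zeros as 0.1 = 0.1×ln 0.1 + 0.4×ln 5 + 0.5×ln 6 − ln 5 = −0.300, a ratio of 0.741.
- With zeros set to 0.5 the ratio is 0.870; with zeros set to 1 it is 0.933.
- Zeros are not essential. If arm B is split equally over 2, 4, 6 and 8, its mean is again 5, but the ratio is 0.885.

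**4. Does a ratio fix the points?** Assuming a proportional effect, a ratio of 0.90 is 0.10×4 = 0.4 points at a placebo mean of 4, and 0.10×10 = 1.0 point at a mean of 10.

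**5. Size for a true 1-point lower mean.** Assumed: negative-binomial scores on 0–52, placebo SDs 4.0, 4.5 and 5.0, the same dispersion parameter in both arms, zeros as 0.1 unless stated. The last column is (1 − ratio) × placebo mean.

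| Placebo → active mean | True ratio of means | Log-scale ratio, zero = 0.1 | Log-scale ratio, zero = 0.5 | Points implied (zero = 0.1) |
|---|---|---|---|---|
| 5.5 → 4.5 | 0.818 | 0.785 | 0.811 | 1.18 |
| 8 → 7 | 0.875 | 0.860 | 0.865 | 1.12 |
| 10 → 9 | 0.900 | 0.891 | 0.893 | 1.09 |

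**6. Weight of the zero rule, if it applies.** ln 1 − ln 0.1 = 2.303 = ln 10 − ln 1, so a change from 0 to 1 counts as much as a change from 1 to 10. The share of the marginal log variance due to zeros is P0×(ln 0.1 − mean log)²/Var(log). At mean 4 (SD 3.5), zeros are 11.4% of scores and supply 63% of that variance. At mean 10 (SD 5.0), they are 0.2% and supply 12%. The rule matters mainly if scores are low.

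**The case against.** The strongest reply is that the log scale was chosen for a reason. Both documents say the residuals do not look normal for Part I in the PPMI data, and the protocol itself puts the Part II regardless-of-ST analysis on the log scale. This explains the choice but does not settle it: the SAP cites the same normality concern for the absence-of-ST Part I analysis and still keeps raw scores as the main model there, with logs as sensitivity.

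Four further points stand in part:

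- A treatment effect with a 95% CI will be reported. It is on the log scale; what is missing is the adjusted difference in points.
- The absence-of-ST model is also refitted on logs, so the two ST strategies can be compared log to log. Only the comparison in points is lost.
- In the negative-binomial illustration the direction is preserved and the size is off by about 9 to 18%. These calculations are marginal, whereas the planned model adjusts for baseline score, and part of the effect comes from the zero rule rather than from the log scale itself.
- SAP Table 1-2 labels the regardless-of-ST subscale summaries supplementary. SAP Table 1-1, its footnote and 5.3.2.1.8 all treat Part I as secondary, as does Protocol Table 9-2.

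The study is described as exploratory, with one primary estimand and no multiplicity adjustment, which limits the consequence.

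**Conclusion.** The concern holds. SAP 5.3.2.1.8 estimates a difference in mean logs for an estimand that both documents define as a difference in means, and that the protocol wants in scale units at Month 18. This follows from the text alone and does not depend on any assumed distribution or on the zero rule.

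The practical size is uncertain because the documents give no Part I mean, SD or share of zeros. Under the assumed distributions it is modest; it grows when scores are low or when the arms differ in spread or in the share of zeros. No primary or key secondary result changes. The plan should be corrected, mainly because the correction is so cheap.

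**What to change.** Before unblinding, amend SAP 5.3.2.1.8 as follows:

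- Fit the same repeated-measures model (treatment, visit, treatment by visit, gender, age, baseline Part I, ARH1 covariance) to untransformed Part I scores with post-ST data kept. Report the adjusted differences at Months 12 and 18 with 95% CIs as the secondary result.
- Keep the log model as a sensitivity analysis. State that it is back-transformed to a ratio and which zero rule applies. A less extreme value than 0.1 would be preferable but is optional.
- If a log-only analysis is intended, redefine the estimand as a ratio and list the change in Appendix 2.

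The Part II supplementary analysis needs no change, because the protocol specifies the log scale there. The cost is SAP wording and one more run of an existing model.
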